12.3.13.1. Pre-treatment Adverse Events

An AE that starts after the subject signed the Informed Consent Form and prior to the first dose of IMP.

12.3.13.2. Treatment Emergent Adverse Events

A treatment emergent adverse event is any adverse event occurring after the administration of the IMP and within the time of residual drug effect, or a pre-treatment adverse event or pre-existing medical condition that worsens in intensity after administration of the IMP and within the time of residual drug effect.

The time of residual drug effect is the estimated period after the administration of the IMP, where the effect of the product is still considered to be present based on pharmacokinetic, pharmacodynamic or other substance characteristics. The residual drug effect is generally accepted to be 5 times the terminal half-life. The terminal half-life of imlifidase is expected to be within the range of approx. 100 hours, i.e. in this study the residual drug effect is likely to be well within the 29 Day assessments. All AEs occurring up to Day 29 are regarded as treatment emergent.

12.3.13.3. Post-treatment Emergent Adverse Events

A post-treatment emergent adverse event is any adverse event occurring after the time of residual drug effect of the IMP, i.e. between the end of the treatment period, visit 8, and the follow-up visit 11.

12.3.14. Analysis of Other Safety Variables

The clinical safety laboratory tests, vital signs, and ECG parameters will be summarised for both absolute values and changes from baseline. Values outside the reference ranges will be flagged in listings.

12.3.15. Immunogenicity

Anti-implifidase antibody data will be summarized by time point and presented using listings.

12.4. Determination of Sample Size

Due to the exploratory nature of the study, there is no formal statistical hypothesis. The difference between treatments for the reduction of DSA will however be presented with 95% confidence interval. A sample size of 20 implifidase and 10 PE subjects is proposed.

In two previous implifidase studies, 14-HMedIdeS-04 and 15-HMedIdeS-06, the IgG reduction for 5 days was 90% and 93% respectively. The corresponding standard deviations are 6% and 4% respectively. Assuming a similar variability in the PE treatment arm, the expected width of the 95% CI for the difference in DSA reduction will be around 8% point. This supports that 20+10 patients are appropriate. Also, the sample size is in line with experience from previous similar Phase II studies with other compounds to obtain adequate safety, tolerability and PK data to achieve the objectives of the study.

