A total of 30 subjects will be included in the study distributed as 20 subjects in the imlifidase arm and 10 subjects in the PE arm. The sample size is not based on a formal calculation but with 20+10 subjects the expected width of the 95% CI of the difference in DSA reduction at any timepoint during the 5 days following the start of treatment (primary endpoint) is 8% point. This expected width is considered acceptable for evaluating a possible difference or similarity between the two treatments.

Diagnosis and main criteria for inclusion/exclusion

Main inclusion criteria are:

- Male and/or female donor kidney recipients, age ≥ 18 years at the time of screening
- Presence of DSA(s)
- Meet the Banff 2017 criteria for active or chronic active AMR
- At least 25% rise in serum creatinine compared to last individual value taken prior to the AMR. Patients with delayed graft function and AMR within 10 days after transplant (confirmed by kidney biopsy) can be included regardless of serum creatinine level

Main exclusion criteria are:

- Previous treatment with imlifidase
- Previous high dose IVIg treatment (2 g/kg) within 28 days prior to inclusion
- Subjects with significantly abnormal general serum screening lab results, judged inappropriate for inclusion in the study by the investigator
- Clinically relevant active infection(s) as judged by the investigator
- Any condition that in the opinion of the investigator could increase the subject's risk by participating in the study such as severe immune deficiency and severe cardiac insufficiency (New York Heart Association (NYHA) Class IV) or severe uncontrolled heart disease

- Known allergy/sensitivity to imlifidase, IVIg and/or rituximab and the respective excipients
- Patient unable to tolerate treatment with plasmapheresis or immunoadsorption, as judged by the investigator
- Positive PCR test for SARS-CoV-2 virus infection
- Current diagnosis or history of thrombotic thrombocytopenic purpura (TTP), or known familial history of TTP

Medicinal Product(s)

Imlifidase is provided as a freeze-dried powder for concentrate for solution for infusion, 11 mg per vial. After reconstitution with sterile water for injection, the concentrate contains 10 mg/mL imlifidase. The concentrate will be added to 50 mL sodium chloride 9 mg/mL (0.9 %) solution for infusion and administered as an infusion.

PE will be prepared and administered according to standard at each site.

Duration of treatment

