Study 14-HMedIdeS-04 was an investigator-initiated phase I/II, single arm, exploratory study in the US. Patients received a single dose of 0.24 mg/kg imlifidase in addition to pre-treatment with rituximab and IVIg. Patients were eligible for inclusion if they had a panel reactive antibodies (PRA) > 50% and a positive crossmatch test against their available DD or had DSA(s) before imlifidase treatment. The study enrolled 17 patients all being transplanted.

Study 15-HMedIdeS-06 was a Phase II study in the US and EU. The study enrolled patients with DSAs and a positive crossmatch test to their available LD or DD. A total of 18 patients were enrolled and transplanted with a kidney from a DD (13) or LD (5). Enrolled patients were treated with imlifidase on day 0. In addition to imlifidase, patients were given high dose IVIg (2 g/kg, maximum of 140 g) on day 7 and rituximab on day 9. DSA levels were monitored pre- and at several time points after imlifidase dosing. Safety, including kidney function, was monitored at multiple time points up to 180 days after treatment. Pharmacokinetics (PK), Pharmacodynamics (PD) and Anti-Drug Antibody (ADA) were measured.

Two studies with imlifidase are ongoing:

1. A phase II study to evaluate the efficacy and safety of imlifidase in anti-GBM disease (Glomerular Basement Membrane/Goodpasture's disease) with adverse renal prognosis (15-HMedIdeS-10, EudraCT no. 2016-004082-39)
2. A prospective, observational long-term follow up study of patients treated with imlifidase prior to kidney transplantation (17-HMedIdeS-14, FDA IND 128074)

Study 15-HMedIdeS-10 is an ongoing investigator initiated multi-centre, open-label Phase II study conducted in EU. The study will enroll 15 patients. Imlifidase 0.25 mg/kg is given IV over 30 min to patients with severe anti-GBM disease on background of standard care consisting of pulse methylprednisolone, oral prednisolone/prednisone and intravenous cyclophosphamide combined with PE.

Study 17-HMedIdeS-14 is an ongoing, five year, follow up, observational study. Up to 46 subjects who have participated in previous studies, received imlifidase and been transplanted will be enrolled.

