7.1.1. Determination of donor specific antibodies

Samples for determination of DSAs and HLA-antibodies will be analyzed in a single antigen bead assay (HLA-SAB) as well as in functional assay e.g. C1q or C3d assay. These assays allow determination of the mean fluorescence intensity (MFI) of antibodies in subject serum reacting to an array of individual HLA immobilized to beads. Analyses of HLA antibodies, including DSA, will be performed centrally. The date and actual time of collection of each sample will be recorded in the eCRF. DSAs for each patient will be identified by respective site. DSAs collected in standard of care at other timepoints will also be recorded in the eCRF

DSA taken at screening will also be analysed at the local lab at each site, in addition to centrally, for determination of presence of DSA(s) for inclusion.

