12.3. Statistical Analysis of Endpoints

12.3.1. Primary efficacy endpoint

The primary endpoint is the maximum reduction in DSA (MFI sum for relevant DSAs) at any time point during the 5 days following the start of treatment. A subject will have at least one DSA and a DSA is considered relevant if it is at least 1000 MFI pre-dose. The reduction is derived as follows:

- 1) Calculate the reduction (%) in sum of DSAs as $100 \times (DSA_0 - DSA_t) / DSA_0$ for each subject and time point. Only DSAs with a pre-dose MFI of 1000 or more will be included in the calculations
- 2) Find the time point with maximum reduction within 5 days for each subject
- 3) The maximum reduction per subject will give a single value as the primary endpoint for the subject

Where DSA_t is the analysis result in total MFI for relevant DSAs at time t.

Due to the exploratory nature of this study, no formal hypothesis will be tested. The difference in reduction between the two treatments will be presented with 95% CI. Each subject will be given equal weight in the calculation of the treatment difference irrespective of number of DSAs for the subjects.

A summary table showing the proportion of reduction of DSAs calculated per subject will also be presented.

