2.2 Determination of sample size

No formal calculation has been done for the sample size. A sample size of totally 30 patients is chosen where 20 patients are treated with imlifidase and 10 patients are treated with PE.

The standard deviations for the two previous studies 14-HMedIdeS-04 and 15-HMedIdeS-06 can be considered to argue for the sample size of 30 patients. The standard deviations for the reduction of the IgG were 6% in the 14-HMedIdeS-04 and 4% in the 15-HMedIdeS-06 study. If the standard deviations are assumed to be similar in this study, it will give approximately an 8% point wide Confidence Interval (CI) when the sample size on 10+20 patients are considered. The 8% point wide of the CI is an acceptable wide and therefore the sample size on 30 patients can be used.

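### Does the 8-point expected CI width for the DSA difference need correcting because it is built on standard deviations of IgG reduction?

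*Protocol*

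**What the plan says.** Protocol 12.4 says that there is no formal hypothesis and proposes 20 and 10 patients. It cites mean IgG reductions of 90% and 93% over 5 days in studies 14-HMedIdeS-04 and 15-HMedIdeS-06, with SDs of 6% and 4%. "Assuming a similar variability in the PE treatment arm", it concludes that "the expected width of the 95% CI for the difference in DSA reduction will be around 8% point". It adds a second reason for the sample size: experience with similar Phase II studies in obtaining adequate safety, tolerability and PK data.

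The synopsis (Number of subjects) says that the size does not come from a formal calculation, and then that the expected width of the interval "of the difference in DSA reduction at any timepoint during the 5 days following the start of treatment (primary endpoint) is 8% point". It calls this width acceptable and gives no SD.

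SAP 2.2 names the source: "The standard deviations for the reduction of the IgG were 6% in the 14-HMedIdeS-04 and 4% in the 15-HMedIdeS-06 study". It makes the 8-point width conditional on similar SDs in this trial.

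The variable to be analysed is, in Protocol 12.3.1, "the maximum reduction in DSA (MFI sum for relevant DSAs) at any time point during the 5 days following the start of treatment", as a percentage of the pre-dose sum over DSAs of at least 1000 MFI. SAP 4.6.1 takes the confidence interval from an ANOVA with treatment as the fixed effect.

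**The concern.** The SDs describe one variable and the interval describes another. Total serum IgG is measured by an electrochemiluminescence immunoassay (Protocol 7.1.2). The primary endpoint is the largest percentage fall in summed single-antigen-bead MFI (Protocol 7.1.1 and 12.3.1). The documents link removal of IgG and of DSA in qualitative terms, but give no SD of DSA reduction for either arm and no SD of any kind for PE. Protocol 12.4 states the assumption that carries the SD from one arm to the other. It does not state the one that carries it from IgG to DSA. The synopsis states neither.

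For study 15-HMedIdeS-06, Protocol 1.1 says that "DSA levels were monitored pre- and at several time points after imlifidase dosing", so a more direct SD might exist, yet only the IgG value is used.

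The 8 points is the only precision figure given for the primary endpoint. If the SD of DSA reduction were well above 5 in either arm, the interval would be wider than readers were led to expect.

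**Working it through.** **Inputs.** n = 20 and 10 (Protocol 12.4). SDs of 4 and 6 points (Protocol 12.4, SAP 2.2). Pooled variance on 20 + 10 − 2 = 28 degrees of freedom, which is what the ANOVA in SAP 4.6.1 uses. The interval is taken as two-sided, with t(0.975, 28) = 2.0484.

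**Formula.** Full width = 2 × t × SD × √(1/20 + 1/10) = 2 × 2.0484 × 0.3873 × SD = 1.5867 × SD.

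**The plan's own figure.** The documents print 4 and 6 but no combined value. Three natural ways to combine them are:

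| Common SD | How obtained | Width (points) |
|---|---|---|
| 5.00 | midpoint of 4 and 6 | 7.93 |
| 5.07 | √((16×36 + 17×16)/33), with 17 and 18 patients (Protocol 1.1) | 8.04 |
| 5.10 | √((36 + 16)/2) | 8.09 |

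All round to 8, so the figure is reproduced. A width of exactly 8 needs a common SD of 8/1.5867 = 5.04.

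**Range on the printed SDs.** SD 4 gives 1.5867 × 4 = 6.35. SD 6 gives 1.5867 × 6 = 9.52.

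**If PE is more variable.** The documents give no PE value, so the SDs of 10 and 20 below are assumptions that show sensitivity only. With an imlifidase SD of 5, the pooled SD is √((19×25 + 9×SD_PE²)/28):

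| Assumed PE SD | Pooled SD | ANOVA width (points) |
|---|---|---|
| 5 | 5.00 | 7.93 |
| 10 | √(1375/28) = 7.01 | 11.12 |
| 20 | √(4075/28) = 12.06 | 19.14 |

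The figure is therefore sensitive to the PE input. That is the assumption Protocol 12.4 does declare.

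**What a reader is told.** In Protocol 12.4, consecutive sentences name IgG reduction, give its SDs, and then state the width for DSA reduction. The substitution is visible on the page, although it is not labelled as an assumption. SAP 2.2 names IgG and attaches the condition of similar SDs.

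**What depends on the figure.** Protocol 12.3.1 and SAP 4.6.1 test no hypothesis, and the plan sets no margin or decision rule on the width. The ANOVA interval is computed from the observed residual variance, so a wrong planning SD cannot carry over into the reported result.

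**The case for a change.** The best case for a change is that, with no hypothesis test, expected precision is the plan's only quantitative argument that 30 patients can inform the comparison. Both the synopsis and Protocol 12.4 use it that way. The assumption of equal variability is also not obviously safe. Imlifidase is one fixed weight-based dose, whereas PE is 5 to 10 sessions at the investigator's discretion, run to local standards at about 14 sites, with immunoadsorption allowed as a substitute. An exploratory aim excuses the absence of a power calculation. It does not excuse a precision figure that the synopsis gives without a condition.

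Part of this stands. The IgG-to-DSA step is not written down as an assumption, the synopsis gives no condition, and one number is printed where the plan's own SDs span 6.35 to 9.52.

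The rest does not carry. Differences in how PE is delivered make a larger SD plausible but do not establish one, and the documents contain no figure to put in its place. That DSA was monitored in 15-HMedIdeS-06 does not show that an SD for this particular endpoint was available. The synopsis is a summary, it disclaims a formal calculation in the same sentence, and 12.4 supplies the basis. Widths for assumed PE SDs would be as unsupported as the value they replaced.

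**Conclusion.** No change is needed. The expected width of about 8 points is correct for a common SD of about 5, and the plan's two SDs bracket it at 6.35 and 9.52. The one omission is a clause saying that the IgG SDs are taken to hold for maximum DSA reduction. A statistician reading 12.4 or SAP 2.2 would supply it, because the source variable is named beside the result. Writing it down would alter neither the sample size, nor the analysis, nor any conclusion, and the safety, tolerability and PK rationale for 30 patients stands apart from it.

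This rests on three things: the trial stays descriptive, with no rule tied to interval width; the reported interval uses the observed variance, as SAP 4.6.1 plans; and the documents hold no evidence that the SD of DSA reduction differs from about 5 in either arm. If it proves larger, the reported interval will show that directly. The 8 points should be read as a planning value and not as a promise of precision.

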13. CHANGES IN STUDY CONDUCT OR PLANNED ANALYSES

Any changes and deviations to plans described in the protocol and in the SAP must be documented.

13.1. Protocol Amendment(s)

Any change to this protocol will be documented in a protocol amendment, issued by Hansa Biopharma, and agreed upon by the investigator and Hansa Biopharma prior to its implementation. Protocol Amendments and documents updated as a result of the Protocol Amendment must not be implemented until all approvals (IEC/IRB and RAs, if applicable) have been obtained.

Changes to the protocol to eliminate immediate hazard(s) to study subjects may be implemented prior to IEC(s)/IRB(s) and RA approval.

13.2. Protocol Deviations

Under working conditions, deviations from the protocol may occur. If deviations from the protocol occur, the investigator must inform the monitor, and the implications of the deviation must be reviewed, discussed and documented on the Protocol Deviation Form. Deviation reports and supporting documentation will be kept in the investigator site file and the study master file.

13.3. Statistical Analysis Plan

Any changes to the SAP will be described in the Clinical Study Report and/or in the Statistical Report.

13.4. Premature Termination or Suspension of the Study

If the study is prematurely terminated or suspended for any reason, the investigator/institution should promptly inform the subjects and should assure appropriate therapy and follow-up.

If the investigator terminates or suspends a study without prior agreement of Hansa Biopharma, the investigator should inform the Institution where applicable. The investigator/institution should promptly inform Hansa Biopharma and should provide Hansa Biopharma with a detailed written explanation of the termination or suspension. If Hansa Biopharma terminates or suspends a Study, the investigator should promptly inform the Institution where applicable. In both cases Hansa Biopharma will promptly inform the RA and IEC/IRB and provide them with a detailed written explanation of the termination or suspension.

If the RA or IEC/IRB terminates or suspends its approval/favourable opinion of a study, Hansa Biopharma should inform the investigators and institutions (where applicable) and provide them with a detailed written explanation of the termination or suspension.

14. REPORTING AND PUBLICATION

14.1. Clinical Study Report

The results from this study will be reported in a clinical study report (CSR) within one year after end of study (see section 4.6). This will be prepared by Hansa Biopharma and submitted for comments and signature to the coordinating (signatory) investigator(s).

14.2. Confidentiality and Data Ownership

Any confidential information relating to the IMP or the study, including any data and results from the study will be the exclusive property of Hansa Biopharma. The investigator and any other persons involved in the study will protect the confidentiality of the proprietary information belonging to Hansa Biopharma.

14.3. Publications

14.3.1. Publication Policy

At the end of the study, one or more manuscripts for joint publication may be prepared in collaboration between the investigator(s) offered authorship and Hansa Biopharma.

Any external CRO or laboratory involved in the conduct of this study has no publication rights regarding the study.

14.4. Public disclosure

The study will be registered in a public clinical trials registry i.e. the U.S. National Institutes of Health register ClinicalTrials.gov and EU Clinical Trials Register if the study is conducted in Europe.

15. ETHICAL AND REGULATORY ASPECTS

15.1. Ethical Conduct of the Study

This study will be conducted in accordance with ICH GCP, the approved protocol and applicable regulatory requirements.

The responsibilities of Hansa Biopharma, the monitor and the investigator are defined in the ICH GCP guideline and applicable regulatory requirements in the country where the study takes place.

15.2. Liabilities and Insurance

Hansa Biopharma is, as sponsor, responsible for ensuring appropriate general/product liability insurance and, as required in accordance with applicable laws and regulations, country-specific liability insurance coverage for claims made by a study subject for injury arising from the subject's participation in the study.

15.3. Independent Ethics Committee(s) and Institutional Review Boards

All ethical and regulatory approvals must be available before a subject is exposed to any study-related procedure, including screening tests for eligibility.

According to applicable regulatory requirements Hansa Biopharma will:

- obtain approval from or notify the relevant IEC(s)/IRB(s) of the protocol, any amendments, the Subject Information Sheet/Informed Consent Form and any advertisements etc.
- send periodic updates to the IEC(s)/IRB(s) if applicable
- provide investigator(s) with an accurate and complete record of all submissions to the local IEC/IRB. The copies should be filed in the investigator file.

Hansa Biopharma will keep an updated list of submission and approval dates of all documents submitted to IEC(s)/IRB(s).

15.4. Regulatory Authority(ies)

According to applicable regulatory requirements Hansa Biopharma will send required documents to the RAs. Hansa Biopharma will keep an updated list of submission and approval dates of all documents submitted to RAs.

Before initiating the clinical study, the Sponsor (or the sponsor and the investigator, if required by the applicable regulatory requirement(s)) should submit any required application(s) to the appropriate authority(ies) for review, acceptance, and/or permission (as required by the applicable regulatory requirement(s)) to begin the study. Any notification/submission should be dated and contain sufficient information to identify the protocol.

15.5. Subject Information and Informed Consent

Before any study-related activities and in agreement with applicable regulatory requirements, the investigator must give the subject oral and written information about the study in a form that the subject can understand. Investigator must ensure that the subject is fully informed about the aims, procedures, potential risks, any discomforts and expected benefits of the Study. Before consenting, the subject must be left with ample time to consider and to pose questions.

It must be emphasised that participation is voluntary and that the subject has the right to withdraw from the Study at any time without prejudice.

The original, signed Informed Consent Forms must be kept in the Investigator File.

The subject will receive a copy of the Subject Information and his/her signed Informed Consent Form.

If new information becomes available that may be relevant to the study subject's willingness to continue participation in the study, a new Subject Information and Informed Consent Form will be forwarded to the IEC(s)/IRB(s) (and RAs, if required). The study subjects will be informed about this new information and re-consent will be obtained.

